#### **11.5.3 The Impact of Immediate and Early (6 Months after Diagnosis) Antiretroviral Therapy on the Decay Dynamics of HIV Viral Load**

For men with acute/recent infection plasma VL will be measured at 0, 1, 2, 4, 6, 8, 12, 16, 24, 36 and 48 weeks. Semen specimens and rectal secretions will be collected from all men with acute/recent infection at 0, 1, 2, 4, 6, 8, 12, 16, 24, 36 and 48 weeks and stored. Semen HIV VL will be measured in these samples from 60 (30 acute/30 recent) ART-treated men and 60 (30 acute/30 recent) untreated men using established procedures in the University of Washington Virology Laboratory [177, 178]. This sample size is adequate to detect a 1.0-1.5  $\log_{10}$  change in VL associated with ART based on the following: semen viral load peaks about 30 days after infection, with mean 4.5 and standard deviation 1.6 ( $\log_{10}$  copies/ml) [185]. We compute the power of a two-sample t-test comparing two arms (ART vs. no ART) to detect significant difference with type I error 5%. With 30/group we have 66% power to detect a 1.0  $\log_{10}$  change and 94% power to detect a 1.5  $\log_{10}$  change based on a single viral load measure at peak per subject. The power would be greater if we use any summary measure of individual's multiple viral loads, e.g., mean across different time points.) We will seek separate funding to analyze additional samples, including rectal secretions. VL in semen and rectal secretions will be more informative for modeling the potential impact of ART on infectivity during this period than plasma VL as these 3 measures are only modestly related [177, 178].

The viral load trajectory will be plotted for each subject and for plasma, semen and rectal secretions separately. The mean trajectory and its confidence interval will be computed stratified by randomized arm and by acute or recent infection. The first-order rate of decay, the area under the curve, the peak viral load, and the lowest viral load will be computed for each subject and compared across arms. Multiple testing adjustment will be applied to control type I error.

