### **Primary Objectives**

1. To estimate the impact of immediate and deferred (24 weeks after study enrollment) antiretroviral therapy (ART) on the decay dynamics of HIV viral load in plasma, semen and rectal secretions from individuals with early HIV infection;
2. To investigate the impact of drug and alcohol use on HIV transmission by examining and modeling the role of MSM and transgender women with substance abuse disorders in transmission clusters identified through partner tracing and phylogenetic analysis.

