##### **6.3.1.3 Duration**

Those participants, who have started their participation in the study before the approval of **Amendment Letter #1** in this study protocol, will continue their participation as originally programmed.

Once the Amendment Letter #1 is approved for this study protocol, the participants who have been diagnosed with **acute HIV infection**, and decide to participate in the study will receive treatment duration of 48 weeks.

For the people who are diagnosed with **recent HIV infection** and decide to participate, treatment will depend on which arm they are assigned to:

Arm 1 will receive study treatment for 48 weeks. Arm 2 will receive no treatment for 24 weeks and then receive 24 weeks of study treatment. However, if during the first 24 weeks of no treatment, clinical, virologic, or immunologic criteria of treatment initiation are met, subject will be offered treatment initiation. ART will be provided by the study for the duration of the time that the participant remains in the study. At the end of study, participants will continue ART from other sources.

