Chemistry/LFT				X		X	X			X							X	
Lipid panel	X***						X			X							X	
Urinalysis	X			X			X			X							X	
Hepatitis B serology																		
STI testing	X						X			X							X	
CD4+/CD8+ cells count	X			X			X			X					X		X	
Plasma HIV-1 RNA	X	X	X	X	X	X	X	X	X	X					X		X	
Semen and rectal secretion collection	X	X	X	X	X	X	X	X	X	X					X		X	
Screening questionnaire - Demographics	X																	
AUDIT	X																	
Interviewer – Monthly questionnaire*	X			X		X	X	X	X				X	X	X	X	X	
Quarterly questionnaire**	X					X			X					X			X	
Pharmacy Refills				X		X	X	X	X				X	X	X	X	X	
Hair Sample	X					X			X					X			X	
Blood volumes (ml) for participants with immediate treatment	160	60	60	71.5	10	121.5	21.5	110	10	121.5	50	50	50	100	13	100	0	121.5
Blood volumes (ml) for participants with deferred treatment	230	60	60	71.5	0	201.5	21.5	190	10	201.5	50	50	50	100	13	100	0	121.5

\*Monthly interviewer-administered questionnaire containing: Timeline Follow Back (alcohol use and sexual behavior), Visual analog scale for ART adherence, and Medication adherence program choices

\*\*Quarterly questionnaire containing: Drug and alcohol use (drug use history, DAST 10, drinking expectancies); Mental health and wellbeing (RAND 12, Social support scale, Stigma scale, Stigma and disclosure, Partner notification, Intimate partner violence, 10 item CES-D, CID Mental health items on anxiety, stress & coping; Medical care (Hospitalization and ER use, Barriers to care, Access to care, Self-efficacy for ART use). \*\*\* These will be done within 72 hours.

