#### **7.4.3.8 Virologic Studies**

1. Plasma HIV-1 RNA

All HIV-1 RNA testing will be performed using the Abbott *m2000 RealTime* System (Abbott Molecular) at the IMPACTA PERU Clinical Trials Unit Central Laboratory, which

is certified by the U.S. NIH/NIAID/DAIDS Virology Quality Assurance (VQA) Program. The baseline value will be the HIV-1 RNA level at the entry evaluation.

The results from the analysis of Plasma HIV-1 RNA for the visits 0, 12, 24, 36, and 48 will be available at the next follow-up visit to guide the medical management decision-making for each participant, according to the HIV management standards.

The plasma samples for RNA HIV-1 determination from visits 1, 2, 4, 6, 8, 16, and 20 will not be processed in real time. Since these determinations are exclusively research purposes, the samples will be processed at a later time.

2. **Phylogenetic Analyses**

HIV-1 sequencing and phylogenetic analysis will be performed at The University of Washington Molecular Genetics Laboratory

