### **11.1 OBJECTIVES**

#### **11.1.1 Primary Objectives**

1. To estimate the impact of immediate and deferred (6 months after diagnosis) ART on the decay dynamics of HIV viral load in plasma, semen and rectal secretions from individuals with early HIV infection;

2. To investigate the impact of drug and alcohol use on HIV transmission by examining and modeling the role of MSM and transgender women with substance abuse disorders in transmission clusters identified through partner tracing and phylogenetic analysis.

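### No viral load is scheduled between weeks 24 and 36, so early decay under deferred ART can only be bounded and the planned comparison of decay rates across arms depends on an estimator the plan does not define

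*Combined protocol and SAP*

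**What the plan says.** The primary objective in Section 2 is "To estimate the impact of immediate and deferred (24 weeks after study enrollment) antiretroviral therapy (ART) on the decay dynamics of HIV viral load", and Section 11.1.1 repeats it with a different anchor: "To estimate the impact of immediate and deferred (6 months after diagnosis) ART on the decay dynamics of HIV viral load". Both cover plasma, semen and rectal secretions. Under Section 6.3.1.3, "Arm 2 will receive no treatment for 24 weeks and then receive 24 weeks of study treatment".

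Section 11.5.3 sets the plasma grid: "For men with acute/recent infection plasma VL will be measured at 0, 1, 2, 4, 6, 8, 12, 16, 24, 36 and 48 weeks". The other compartments share it: "Semen specimens and rectal secretions will be collected from all men with acute/recent infection at 0, 1, 2, 4, 6", and the list then runs on through the same weeks, with 36 directly after 24. Section 7.4.3.8 agrees for plasma. On real-time results: "The results from the analysis of Plasma HIV-1 RNA for the visits 0, 12, 24, 36, and 48 will be available". On the rest: "The plasma samples for RNA HIV-1 determination from visits 1, 2, 4, 6, 8, 16, and 20 will not be processed in real time". Neither list has a visit between weeks 24 and 36.

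The post-amendment schedule in 7.4.1 has visits at weeks 25, 26, 28 and 32. Its row "Blood volumes (ml) for participants with deferred treatment" shows 50, 50, 50 and 100 mL there, but no HIV-1 RNA and no semen or rectal collection is marked at those weeks.

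For the analysis, 11.5.3 computes four summaries per subject (first-order decay rate, area under the curve, peak and lowest viral load) and compares them across arms. It gives no time origin or window for the decay rate and no rule for values below the assay limit.

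**The concern.** The dense early sampling is tied to enrolment, which coincides with ART start only for those treated immediately. In Arm 2 it falls in the untreated period, and the first 12 weeks on ART, when most of the fall is likely to happen, contain no measurement until week 36. One half of primary objective 1, the early decay under deferred ART, therefore has almost no data behind it.

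The risk is a false comparison as well as an imprecise one. A per-subject slope computed on two such different grids can differ between arms when the biology is the same, and the result could be read as an effect of delaying treatment.

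Analysis cannot repair this afterwards. Section 7.4.3.11 provides for plasma storage only at time points where an HIV-1 RNA level is required, so usable plasma from weeks 25 to 32 is not assured. Semen and rectal samples that were never collected cannot be recovered.

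**Working it through.** **1. The plan's own figure.** Section 11.5.3 gives 66% and 94% power for 1.0 and 1.5 log10 with 30 per group, SD 1.6 and type I error 5%. The noncentrality is (difference/1.6) × √(30/2), that is 2.42 and 3.63. A two-sided t-test on 58 df gives 66.3% and 94.6%. The figures reproduce. They concern ART against no ART at the semen peak, not decay rates, and the week 24-36 gap does not touch them.

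**2. On-ART samples in the first 12 weeks of treatment (11.5.3 grid).**
- Arm 1: weeks 1, 2, 4, 6, 8 and 12, so six.
- Arm 2, starting at about week 24: week 36 only, so one. Week 48 is about 24 weeks on ART.

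**3. Cap on the Arm 2 slope.** Inputs are assumptions: a start V0 of 4.0 to 5.5 log10 and a floor of 50 copies/mL (log10 50 = 1.70). The documents give no week 24 viral load and no detection limit. The 4.5 in 11.5.3 is a semen mean at peak, and 50 copies/mL is the plasma suppression threshold used in Sections 3.3.3 and 4.4.

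Largest observable slope = (V0 − 1.70)/12:
- 4.0: 0.19 log10/week
- 4.5: 0.23
- 5.0: 0.28
- 5.5: 0.32

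This holds however fast the true decay is.

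**4. Slope taken to the first value at the floor.** Let T be the weeks on ART needed to reach the floor with log-linear decay. The true rate is (V0 − 1.70)/T and Arm 2 shows (V0 − 1.70)/12, so the ratio is 12/T.

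| T (weeks, assumed) | True rate at V0 = 4.5 | Arm 2 shows | Ratio |
|---|---|---|---|
| 1 | 2.80 | 0.23 | 12 |
| 2 | 1.40 | 0.23 | 6 |
| 4 | 0.70 | 0.23 | 3 |
| 8 | 0.35 | 0.23 | 1.5 |
| 12 | 0.23 | 0.23 | 1 |

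**5. Least squares on all on-ART points, same true decay in both arms.** Take V0 = 4.5 and an assumed 1.0 log10/week.
- Arm 1, weeks 0, 1, 2, 4, 6, 8, 12: values 4.5, 3.5, 2.5, then 1.70 four times. Sxx = 265 − 33²/7 = 109.4; Sxy = 59.47 − 33 × 2.471 = −22.07; slope 0.202 log10/week.
- Arm 2, 0 and 12 weeks on ART: (4.5 − 1.70)/12 = 0.233.
- Extended to 24 weeks on ART: Arm 1 (adding weeks 16 and 24) has Sxx = 504.9 and Sxy = −40.4, slope 0.080. Arm 2 (0, 12, 24) gives (4.5 − 1.70)/24 = 0.117.

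Here Arm 2 looks faster. On the schedule's grid, which includes week 20, the 24-week fit gives 0.060 (Arm 1) against 0.117 (Arm 2) at T = 2, and 0.127 against 0.117 at T = 12. The sign depends on the estimator and on T.

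**6. With RNA at weeks 25, 26, 28 and 32** (1, 2, 4 and 8 weeks on ART if the first dose is at week 24). At V0 = 4.5 and T = 4, the slope to the first floor value becomes 0.70 in both arms. At T = 6 it is 2.80/8 = 0.35 in Arm 2 against 2.80/6 = 0.467 in Arm 1, because Arm 2 has no draw at 6 weeks on ART. The added samples remove most of the artefact; the remainder needs a censored-data model.

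**The case against.** The strongest defence is that the trial's randomised question is immediate ART against no ART over weeks 0-24. Section 11.5.3 describes the semen comparison group as untreated, the power statement covers only that contrast, and that period is densely sampled. This stands. Area under the curve, peak, lowest value and suppression at weeks 36 and 48 also remain estimable, as does an average or lower-bound slope in Arm 2. Section 11.5.4 takes viral loads from treated and untreated men for its infectivity estimates and does not name a deferred-ART decay rate. The defence does not remove the commitment in the primary objective and the title of 11.5.3 to decay under deferred ART as well.

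A reader might infer that deferred-ART decay cannot be estimated at all, or that it will appear several-fold too slow. The documents support neither. They give no decay rate and no estimator. A distortion of threefold or more needs suppression within about four weeks and a slope taken to the first floor value; other choices give no distortion or the opposite sign. Section 3.3.3 expects 90% of patients below 50 copies/mL in 4 months, which does not say how many are at the floor at 12 weeks.

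A reader might also think the gap could be closed at no cost by moving Arm 2 collections from weeks 6, 16 and 20. That would thin the randomised comparison in weeks 0-24 and leave no Arm 2 sample between weeks 12 and 24. Nor would it avoid new draws for pre-amendment participants, whose schedule has no week 25 or 26 visit and 0 mL at weeks 28 and 32. Section 4.1 says roughly half of participants had already been enrolled.

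**Conclusion.** The point holds in this form. Sections 11.5.3 and 7.4.3.8 leave about 12 weeks after deferred ART starts without a viral load, against six measurements in the same period of Arm 1. Early decay under deferred ART is therefore not identifiable. For a man suppressed by week 36 the data give only a lower bound, with the observed slope capped at 0.19 to 0.32 log10/week under the assumed starts and floor. A first-order rate compared across arms on these grids can show a spurious difference in either direction. Its size cannot be fixed from the documents: on the slope to the first floor value the factor runs from 1 to 12 as the assumed time to the floor runs from 12 weeks to 1.

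The conclusion about the gap rests on the two text lists, not on the schedule tables, whose columns are partly misaligned in the copy reviewed. It assumes Arm 2 starts at about week 24; men who start earlier under Section 4.2 may have denser data.

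**What to change.** **Sampling.** In 7.4.1, 7.4.3.8 and 11.5.3, add batch research plasma HIV-1 RNA, with plasma storage, for post-amendment Arm 2 participants at the existing week 25, 26, 28 and 32 draws. Keep the week 6, 16 and 20 collections.

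**Analysis.** In 11.5.3, compute on-ART decay from the first-dose date, state the window, and treat values below the assay limit as censored. Compare arms at equal weeks since ART start, as a separate analysis labelled non-randomised, apart from the weeks 0-24 contrast.

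**Claims.** For pre-amendment participants, and for semen and rectal secretions if no early post-start samples are collected, limit the deferred-arm decay claim to a bound and to suppression at weeks 36 and 48.

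**Entries to reconcile.**
- Week 28 in the pre-amendment table: one reading marks RNA and semen/rectal collection, but the blood volume is 0 mL and neither text list has that week.
- Week 20: scheduled and in 7.4.3.8, absent from 11.5.3.
- Week 6 in the post-amendment table: RNA marked, but 0 mL for the deferred group.
- The deferral anchor: Sections 2, 4.1, 4.2 and 11.1.1 variously count from enrolment and from diagnosis, and the choice decides whether the week 24 sample precedes ART.

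**Cost.** A schedule amendment and up to four extra batch plasma assays per post-amendment Arm 2 participant, with no added visits for them. The stated purpose of the 50-100 mL draws is not given, so confirm that plasma can be set aside from them.

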## *Test and Treat Early HIV among MSM and Transgender Women in Lima, Peru*

infection or with symptoms of acute retroviral syndrome. We anticipate testing approximately 2400 MSM and transgender women until July 2015. In Step 2, high risk HIV-1 uninfected MSM with high risk sexual behavior will be tested at variable times (during which they will receive standard HIV prevention education) for incident HIV-1. Roughly, we anticipate re-testing approximately 800 MSM and transgender women per month until July 2015. In Step 3, individuals with acute and recent HIV-1 infection detected at Step 1 or 2; or individuals who have been diagnosed with HIV in any health clinic or laboratory authorized by the Ministry of Health, and that have had a documented negative result in the past three months, will be enrolled in a 48-week randomized, open label clinical trial of the effects on the decay dynamics of HIV viral load in plasma, semen and rectal secretions of immediate vs. deferred (by 24 weeks) ART, unless ART initiation criteria are met earlier. We expect approximately 200-250 MSM and transgender women (roughly 100-125 individuals with acute and 100-125 with recent HIV-1 infection).

Those participants, who have started their participation in the study before the approval of **Amendment Letter #1** in this study protocol, will continue their participation as originally programmed.

Once the **Amendment Letter #1** is approved for this study protocol, the participants who are eligible for Step 3 will be given treatment the following way: 1) those people diagnosed with **acute HIV infection** will be offered immediate ART (just at time of the enrollment visit or during the next 48 to 72 hours) for the duration of 48 weeks. 2) The people who are diagnosed with **recent HIV infection** will be randomized to start immediate ART or defer ART initiation until 24 weeks after HIV diagnosis, all of them followed for 48 weeks after which they will continue ART from other sources.

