in any health clinic or laboratory authorized by the Ministry of Health, and that have had a documented negative result in the past three months, will be enrolled in a 48-week randomized, open-label clinical trial of the effects on the decay dynamics of HIV viral load in plasma, semen and rectal secretions of immediate –ARM 1- vs. deferred (by 24 weeks) –ARM 2- ART, unless ART initiation criteria are met earlier. We expect that approximately 200-250 MSM and transgender women (roughly 100-125 with acute and 100-125 with recent HIV-1 infection) will participate in the study. Those participants, who have started their participation in the study before the approval of **Amendment Letter #1** in this study protocol, will continue their participation as originally programmed. Once the **Amendment Letter #1** is approved for this study protocol, the participants who are eligible for Step 3 will be given treatment the following way: 1) those people diagnosed with **acute HIV infection** will be offered immediate ART (just at time of the enrollment visit or during the next 48 to 72 hours) for the duration of 48 weeks. 2) The people who are diagnosed with **recent HIV infection** randomized to start immediate ART or defer ART initiation until 24 weeks after HIV diagnosis, all of them followed for 48 weeks after which they will continue ART from other sources. Roughly half of these participants have been enrolled to date. These participants will receive Atripla as study drug; participants enrolled after approval of this protocol version will receive Stribild.

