### **6.3 STEP 3**

#### **6.3.1 Regimens, Administration, and Duration**

##### **6.3.1.1 Regimen**

Those participants, who have initiated their participation in the study before the approval of **Amendment Letter #1** in this study protocol, will continue their participation as originally programmed.

Once the **Amendment Letter #1** is approved for this study protocol, the participants who are eligible for Step 3 will be given treatment the following way:

- Those people diagnosed with **acute HIV infection** will be offered immediate ART (just at time of the enrollment visit or during the next 48 to 72 hours) for the duration of 48 weeks.

Weeks 0-48: Co-formulated elvitegravir/cobicistat/emtricitabine/tenofovir disoproxil fumarate (or co-formulated emtricitabine/tenofovir DF/efavirenz) orally once daily.

Those people diagnosed with recent HIV infection will be randomized to one of the following arms:

1. Arm 1:

Weeks 0-48: Co-formulated elvitegravir/cobicistat/emtricitabine/tenofovir disoproxil fumarate (or co-formulated emtricitabine/tenofovir DF/efavirenz) orally once daily.

2. Arm 2:

Week 0-24: No treatment unless Peruvian criteria for initiation of treatment are met.

Week 25-48: Co-formulated elvitegravir/cobicistat/emtricitabine/tenofovir disoproxil fumarate (or co-formulated emtricitabine/tenofovir DF/efavirenz) orally once daily.

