### **11.3 SAMPLE SIZE AND ACCRUAL**

Our goal is to enroll approximately 75-90 men with AHI and 75-90 with RHI in three years, with a target of enrolling 25-50 men with AHI and 25-50 men with RHI per year, or approximately 2-4 men in each group per month. We expect that another 50 men will be identified with acute or recent HIV-1 infection who will either not meet all inclusion requirements or who will not consent to enrollment in the study. Specimens for sequencing will be collected from all men.

Samples for sequencing will be obtained from all identified HIV+ partners of the 200 men with acute/recent infection (we anticipate that not all men will consent to partner tracing). Our initial sequencing efforts will focus on the 100 acutely infected men (75 enrolled plus 25 non-enrolled in immediate/deferred ART study) and their HIV+ partners (especially those with acute or recent HIV infection), testing a total of 400 samples. The first available sample will be sequenced with 454/pyrosequencing and analyzed as described below.

Semen HIV VL will be measured in samples from 60 (30 acute/30 recent) men in the immediate ART group and 60 (30 acute/30 recent) men in the deferred treatment group using established procedures in The University of Washington Virology Laboratory [177, 178]. We will seek separate funding to analyze additional samples, including rectal secretions.

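### Section 11 still plans 30 acute deferred men and an across-arms comparison, although only recent infections are randomised after Amendment Letter #1

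*Combined protocol and SAP*

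**What the plan says.** **Allocation after the amendment.** Sections 2, 4.1 and 6.3.1.1 agree. People with acute infection "will be offered immediate ART (just at time of the enrollment visit or during the next 48 to 72 hours"), for 48 weeks. For recent infection, Section 6.3.1.1 says "Those people diagnosed with recent HIV infection will be randomized to one of the following arms", and Section 2 says these people "will be randomized to start immediate ART or defer ART initiation until 24 weeks after HIV diagnosis". Anyone who started before the amendment stays on the original scheme.

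**Sample size.** Section 11.3 plans semen viral load in 60 immediate-ART men and in "60 (30 acute/30 recent) men in the deferred treatment group". Section 11.5.3 repeats the plan by treatment status: "Semen HIV VL will be measured in these samples from 60 (30 acute/30 recent) ART-treated men and 60 (30 acute/30 recent) untreated men". Its power statement begins "With 30/group we have 66% power to detect a 1.0" log10 change, and gives 94% for 1.5 log10.

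**Analysis.** Section 11.5.3 stratifies the mean viral load trajectories by randomised arm and by infection stage. Four per-subject summaries follow: decay rate, area under the curve, "the peak viral load, and the lowest viral load will be computed for each subject and compared across arms". That sentence neither limits the comparison to randomised men nor repeats the stratification.

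**Enrolment so far.** Section 4.1 says "Roughly half of these participants have been enrolled to date". It gives no split by stage or arm and does not tie the figure to the date of Amendment Letter #1.

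**The concern.** Section 11 does not mention Amendment Letter #1. It was evidently written for a design that randomised both stages, and two things no longer fit.

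First, after the amendment no acute man is assigned to deferral, so the 30 acute deferred men must all have been randomised earlier. The plan does not say whether that many exist.

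Second, the plan does not say where the acute men enrolled after the amendment belong in a comparison of arms. Section 6.3.1.1 gives them no arm. Section 7.4.2.1 nevertheless times their start of treatment from randomisation, and the general descriptions in Sections 4.1 and 5.3.1 still present acute and recent infections together as randomised to immediate or deferred ART.

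This is the between-arm analysis for primary objective 1, and either reading has a cost:

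- **Counted as immediate.** The acute contrast becomes partly non-randomised and non-concurrent, and the pooled arms differ in stage mix. Sections 3.5.3 and 3.6.2 describe high viral load in acute infection and an early burst that usually resolves within two months, so stage can confound peak and decay. Regimen also changes with enrolment period (Section 4.1: Atripla earlier, Stribild later), and Section 3.2 says viral load falls faster on Stribild.
- **Excluded.** The acute stratum may be smaller than the stated power assumes.

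The trial is open label and Section 11.4 has endpoints calculated monthly, so an unsettled analysis set could end up being settled after the data have been seen.

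**Working it through.** **Inputs**

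- SD 1.6 log10, type I error 5%, two-sample t-test, 30 per group, effects of 1.0 and 1.5 log10 (Section 11.5.3).
- Acute totals T of 75 to 90 (Section 11.3) or 100 to 125 (Sections 2 and 4.1).
- Assumptions, because the documents are silent: two-sided test, 1:1 allocation, equal acute and recent totals, no dropout. The share f of acute enrolment that preceded the amendment is unknown, so 25%, 50% and 75% are shown.

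**1. The plan's own figure.** Power comes from the noncentral t distribution with noncentrality δ / (1.6 × √(1/n₁ + 1/n₂)).

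- For 30 v 30 the noncentrality is 1.0 / (1.6 × √(2/30)) = 2.42, giving 66.3%. At 1.5 log10 it is 3.63, giving 94.6%. Both agree with the stated 66% and 94%.
- For 60 v 60 the power would be 92.4% and 99.9%.

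The stated power is therefore for one infection stage, and in the acute stage it depends on 30 deferred men.

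**2. Share needed to supply 30 acute deferred men.** Acute deferred = T × f/2, so the required f is 60/T:

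- T = 75: 80%
- T = 90: 67%
- T = 100: 60%
- T = 125: 48%

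**3. Acute stratum if post-amendment acute men are excluded**

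| f | Acute total | Randomised acute men per arm (T × f/2) | Power at 1.0 log10 | Power at 1.5 log10 |
|---|---|---|---|---|
| 25% | 75–125 | 9–16 | 24–40% | 46–73% |
| 50% | 75–90 | 19–22 | 47–53% | 80–86% |
| 50% | 100–125 | 25–31 | 58–68% | 90–95% |
| 75% | 75 | 28 | 63% | 93% |

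At 75% with larger totals there are 30 or more per arm and the plan is met. Filling the immediate group up to 30 with non-randomised men gives 55% and 88% against 19 deferred, and 59% and 91% against 22. That recovers part of the power but gives up the randomised comparison.

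**4. Stage mix if post-amendment acute men count as immediate.** As fractions of the acute total, acute immediate = 1 − f/2, acute deferred = f/2, and recent = 0.5 in each arm.

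| f | Acute share, immediate | Acute share, deferred | Gap (points) | Acute-immediate men not randomised, (1 − f)/(1 − f/2) |
|---|---|---|---|---|
| 25% | 0.875/1.375 = 64% | 0.125/0.625 = 20% | 44 | 86% |
| 50% | 0.75/1.25 = 60% | 0.25/0.75 = 33% | 27 | 67% |
| 75% | 0.625/1.125 = 56% | 0.375/0.875 = 43% | 13 | 40% |

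**5. Recent stratum.** Recent men are randomised concurrently throughout, so 30 v 30 and its 66% and 94% stand.

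**The case against.** The strongest reply is that the text, read as a whole, already keeps these men out of the arms. Section 6.3.1.1 lists Arms 1 and 2 only under recent infection, Section 6.3.1.3 does the same, and Sections 7.4.2.3 and 7.4.2.4 describe subjects in each arm as having recent infection. Section 7.4.2.1 gives acute subjects and Arm 1 subjects separate sentences. In Section 11.5.3 the arms being compared would naturally be the randomised arms named one sentence before, and the 30 acute/30 recent sampling suggests comparison within stage. On that reading the stage imbalance never arises.

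This is a reasonable reading and probably what was intended, but the text does not secure it. Sections 4.1 and 5.3.1 still describe acute men as randomised, Section 7.4.2.1 still refers to their randomisation, and Section 11 groups men as immediate or ART-treated, which fits post-amendment acute men. The reading also does nothing to supply 30 acute deferred men.

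Several other points stand as limits:

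- Thirty acute deferred men are not impossible, because men randomised before the amendment stay in their arm. The shortfall depends on an unreported count.
- The 30-per-stage figures and the power apply to the semen subsample only. Plasma viral load is measured in all men.
- Section 11.5.3 notes that its power is for a single measure at peak, and that summary measures would give more.
- The transmission modelling in Section 11.5.4 uses viral load by treatment status and does not need randomised arms.

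None of these supplies the missing rule for the analysis set.

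**Conclusion.** The concern holds, and the plan is wrong as written. Sections 11.3 and 11.5.3 describe an acute deferred group that the amended design no longer recruits, and the comparison serving primary objective 1 has no rule for the non-randomised acute men. The mismatch is certain from the text; its numerical size is conditional.

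With 1:1 allocation and equal stage totals, counting those men as immediate opens a gap of 13 to 44 percentage points in acute share between the arms, over pre-amendment shares of 75% down to 25%. Excluding them leaves between 9 men per arm and a fully met plan, with acute-stratum power at 1.0 log10 from 24% up to the stated 66% or slightly more. The gap in the analysis set exists whatever the enrolment count. The problem is confined to the acute stratum and to any contrast pooled over stage. It must be fixed before the between-arm analysis is run.

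**What to change.** 1. In Section 11.5.3, define the between-arm analysis set as men actually randomised: all recent infections, plus acute infections randomised before the amendment. State that the four summaries are compared within, or stratified by, infection stage.
2. Report post-amendment acute men as a separate, non-randomised descriptive cohort. Label any comparison of them with pre-amendment deferred men as non-randomised and non-concurrent, with a different predominant regimen.
3. In Sections 11.3 and 11.5.3, replace the 30 acute deferred or untreated men with the number actually randomised to deferral, and restate the acute-stratum power for that number.
4. Reconcile the reference to randomisation of acute subjects in Section 7.4.2.1, and the general descriptions in Sections 4.1 and 5.3.1, with Section 6.3.1.1.

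Stratifying the recent stratum by enrolment period is optional, since those men were randomised concurrently.

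The cost is protocol and SAP wording and one stratified analysis, with no new patients or procedures. The restated acute size and power may be less favourable than the present figures.
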